1.2 Rationale

This study is intended to provide statistically robust evidence that guided bone regeneration outcomes using a GUIDOR® membrane with allograft is similar or better to outcomes obtained using other commercially available barrier membranes with allograft. It is intended to define in objective and subjective terms the response of the bone and overlying soft tissues to localized ridge augmentation. To fulfill the goals of this project,

the clinical study will seek to enroll patients with a single bound edentulous space that requires ridge augmentation prior to dental implant treatment.

It has been shown that the undisturbed, healed socket will lead to a loss of alveolar bone with a mean width reduction of 3.8 mm and height reduction of 1.24 mm within 6 months (9). Schropp et. al (2003), found, according to subtraction radiography, that by 12 months, the alveolar bone present after tooth extraction decreased by up to 50% of its original width (10). Buser, et. al (1990), reported a mean gain of 1.5-5.5mm of new bone formation 6-10 months post-GBR (11). Based on these studies, a significant difference should be observed, especially between the bone grafting group and the control group.

The goal of guided bone augmentation is to provide an alveolar ridge of sufficient dimension to permit dental implant placement. The healing of these sites should occur with an absence of inflammation and other complications.

This prospective clinical evaluation will enroll sufficient participants to perform statistical analyses of primary objectives. Additional information regarding the presence or absence of inflammation, infection, or other wound healing complications will also be obtained through the projected enrollment.

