Individuals meeting all inclusion and none of the exclusion criteria and that have signed all appropriate consent forms will be further evaluated. Screening will entail evaluation of general dental and systemic health. It will also include a clinical and radiographic assessment of the edentulous site and the adjacent teeth. Pre-existing radiographs (e.g. panoramic and intraoral) can be used but must not be older than 6 months. Subjects with adequate alveolar ridges will immediately be scheduled for Visit 2 provided that they fulfill all inclusion and none of the exclusion criterion.

The following items will be completed during the screening visit:

- Medical, Social, and Dental History
- Oral examination
- Concomitant Medications Use: Concomitant medications which will be collected during this study consist of prescription and OTC drugs except for dietary supplements.
- Confirm radiographic assessment for inclusion and exclusion criteria

Visit 2: Cone Beam Computed Tomography Imaging (2 weeks \pm 4 days from Visit 1)

Small field-of-view cone beam computed tomography (CBCT) imaging will be obtained for all patients at baseline and 6 months following the guided bone regeneration surgical procedure using the Carestream CS9300 System or equivalent system. Images will provide baseline data for horizontal and vertical bone locations. CBCT imaging will be conducted in accordance to institutional standards and technique.

Visit 3: Guided Bone Regeneration Surgery (8 weeks \pm 7 days from Visit 1)

[figure not shown]
Prior to randomization, confirmation and verification of all inclusion and exclusion criteria must be completed.

The time of enrollment for this study is defined at the time the patient signs the informed consent form, meets all inclusion criteria and no exclusion criteria, is randomized and receives study treatment.

Randomization and Stratification

Subjects meeting all inclusion and none of the exclusion criteria will be randomly allocated to group A, B or C. The randomization will be per center and based on smoking status.

Figure 2 Randomization and stratification

Pre-Surgical Procedures

Buccal and crestal photographs of the planned surgical site will be obtained using a Canon 50D digital camera body with a Canon 100mm f/2.8 macro lens and a Canon MR-14EX macro ring flash or equivalent device. The films must be stored in the subject's medical chart.

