3.2.1.3 Procedures for handling incorrect enrolled subjects

Subjects not meeting the inclusion/exclusion criteria for a study should not be enrolled into the study. If a subject is enrolled who does not meet inclusion/exclusion criteria, a protocol deviation will be completed.

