6 STATISTICAL METHODS AND DETERMINATION OF SAMPLE SIZE

6.1 Statistical evaluation – general aspects

A comprehensive Statistical Analysis Plan (SAP) may be prepared before database lock. When using the terminology descriptive statistics it means that number of patients, mean, median, standard deviation, minimum and maximum values will be presented for continuous data and frequencies and percentages for categorical data.

If nothing else is stated, descriptive statistics will be given for each variable in the study and p-values may be complemented by confidence intervals as appropriate. All p-values presented will be two-sided. A p-value less than 5% will be called “statistically significant” but all conclusions will be based on the primary objective and hence multiplicity is accounted for even though careful interpretations are necessary as multiple tests are performed.

Analysis populations are defined as follows:

- The Intent-to-Treat (ITT) population includes all enrolled subjects who underwent guided bone regeneration procedure.
- The Per-Protocol (PP) population includes all enrolled subjects who had successful guided bone regeneration procedure and no major protocol deviations (defined as inclusion/exclusion or informed consent violations.)

The ITT population will be the primary analysis population for all endpoints. Analyses on the PP population will be supportive of the ITT analyses.

Demographics and other baseline characteristics

Demographics and other baseline characteristics will be presented by means of descriptive statistics (by group and in total). Continuous variables will be presented by means of number of observations (N), minimum (min), median, maximum (max), mean, and standard deviation (std). Discrete variables will be presented by frequency and percentage.

Covariates and prognostic variables

No covariates are judged to influence the outcome of the primary or any of the secondary variables.

Handling of dropouts and missing data

Patients dropping out from the trial prior to study end will not be replaced. Data totally missing will not be estimated.

Multicenter

This study is a multicenter study. However, there is not a priori reason to suspect that there will be any qualitative differences between the centers regarding any of the efficacy variables nor regarding the safety variables. Therefore, the primary statistical analyses will not include center in the model.

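### The per-protocol set requires an undefined 'successful' procedure, which permits selection on the trial's own endpoints, while treatment departures do not exclude anyone

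*Combined protocol and SAP*

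**What the plan says.** Section 6.1 defines two analysis sets. For intention to treat: "The Intent-to-Treat (ITT) population includes all enrolled subjects who underwent guided bone regeneration procedure". For per protocol: "The Per-Protocol (PP) population includes all enrolled subjects who had successful guided bone regeneration procedure and no major protocol deviations". Major deviations are limited to two kinds: "no major protocol deviations (defined as inclusion/exclusion or informed consent violations". The intention-to-treat set is primary for all endpoints, and "Analyses on the PP population will be supportive of the ITT analyses".

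No section says what makes a procedure successful, who decides, or when. Section 6.1 says only that a separate SAP may be prepared before database lock, so it does not guarantee that the term will be settled there.

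Three other places bear on the point:

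- Section 3.1 (Visit 3) builds eligibility and consent into enrolment itself: "The time of enrollment for this study is defined at the time the patient signs the informed consent form, meets all inclusion criteria", and the sentence goes on to require that the subject is randomised and treated.
- Section 3.2.1.3 foresees exceptions: "If a subject is enrolled who does not meet inclusion/exclusion criteria, a protocol deviation will be completed".
- Section 1.2 gives the aim of treatment: "The goal of guided bone augmentation is to provide an alveolar ridge of sufficient dimension to permit dental implant placement". It adds that sites should heal free of inflammation and other complications.

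**The concern.** Membership of a per-protocol set should depend on whether the protocol was followed, not on how well the treatment worked. The intention-to-treat definition asks only that the procedure took place; the per-protocol definition asks that it succeeded. The extra word has to carry some meaning, and the only description of what the procedure should achieve (section 1.2) overlaps with ridge dimension, the primary outcome, and with inflammation, infection and soft tissue complications, the secondary outcomes.

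Under section 3.4 the envelope is opened after flap elevation. Any judgement of success is therefore made after randomisation, and the operator knows the arm by then. If poor results were classed as unsuccessful, an arm with more failures would lose its worst values. Agreement or disagreement between the two analyses could then not be read as evidence about protocol adherence.

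The set also omits what it should screen for. Section 4.7 requires deviations in conduct, patient management and assessment to be documented, but section 6.1 does not count them as major. A subject given non-allocated material, or scanned outside the Visit 7 window of 24 weeks ± 7 days (section 3.1), remains in the per-protocol set.

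**Working it through.** **1. The plan's own figure.** Inputs from sections 6.1 to 6.3: difference 0.5 mm, SD 0.5 mm, two-sided alpha 0.05, power 80%, Wilcoxon rank sum test.

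- Normal approximation: n = 2 × (1.960 + 0.842)² × (0.5/0.5)² = 15.7, so 16 per group.
- t-test: 16.7, so 17.
- Divided by the Wilcoxon efficiency of 0.955: 16.71/0.955 = 17.5, so 18.
- With 10% dropout: 18/0.9 = 20.

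The stated 18 and 20 are reproduced, so the same inputs are used below.

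**2. How much the deviation condition removes.** On the literal wording of section 3.1, an enrolled subject has consented and meets every criterion, so a filter for eligibility and consent violations has almost nothing to remove. Section 3.2.1.3 expects some ineligible subjects to be enrolled and logged as deviations; if treated, they would be in the intention-to-treat set and outside the per-protocol set. The two sections conflict, and the content of the filter depends on which is followed.

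**3. What the success condition could do.** The documents give no success criterion and no failure rate. Every fraction below is an assumption.

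*(a) Success means surgery technically completed, unrelated to bone gain.* No bias need arise. Removing 2 or 4 of 20 from one arm at random, with no true difference, leaves the simulated two-sided error at about 4% to 5%.

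*(b) Success means bone change above one threshold applied to all arms, with no true difference.* With 10%, 15% or 20% failing in both arms (20 per arm), the simulated error is 4.5%, 4.9% and 4.8%. There is no inflation.

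*(c) The same common threshold, with a true difference of 0.5 mm.* For an arm with mean μ and threshold c, let a = (c − μ)/0.5. The mean of those kept is μ + 0.5 × φ(a)/(1 − Φ(a)). If 10% of the comparator arm fails, c = −1.2816 × 0.5 = −0.641 relative to the comparator mean:

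- comparator: 0 + 0.5 × 0.1755/0.90 = 0.097;
- better arm: a = −2.28, giving 0.5 + 0.5 × 0.0296/0.989 = 0.515;
- difference: 0.515 − 0.097 = 0.42 mm.

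| Comparator failing | Difference in PP set | Wilcoxon power, 18 per arm before removal |
|---|---|---|
| none | 0.50 mm | about 80% |
| 10% | 0.42 mm | about 72% |
| 20% | 0.36 mm | about 62% |
| 30% | 0.32 mm | about 50% |

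*(d) The lowest values are removed from one arm only, with no true difference.* The mean shift is 0.5 × φ(z)/(1 − q), where q is the fraction removed and z its normal quantile. The error column removes exactly the lowest 2, 3 or 4 of 20.

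| Removed | Shift | Share of 0.5 mm | Two-sided error |
|---|---|---|---|
| 10% (2 of 20) | 0.5 × 0.1755/0.90 = 0.097 mm | 19% | about 9% |
| 15% (3 of 20) | 0.5 × 0.2332/0.85 = 0.137 mm | 27% | about 13% |
| 20% (4 of 20) | 0.5 × 0.2800/0.80 = 0.175 mm | 35% | about 17% |

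Nearly all of the excess error favours the arm that lost its lowest values. A variant with 18 per arm and a fixed cut-off gave about 7% at 10% and 15% at 20%, which is the same pattern.

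**The case against.** A reader might infer three stronger things, and the documents do not support them.

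- **That success is the only condition that does any work.** This follows from the enrolment wording in section 3.1 alone. Section 3.2.1.3 foresees ineligible subjects being enrolled, section 4.7 records such deviations, and section 6.1 makes them an exclusion. What stands is the conflict between 3.1 and 3.2.1.3.
- **That the set does select on outcome.** Beside the intention-to-treat wording, a successful procedure can fairly be read as surgery completed as section 3.1 describes, with the materials placed and primary closure achieved. Section 1.2 makes the outcome reading available, but section 6.1 does not adopt it, and no bone-gain threshold appears anywhere.
- **That the per-protocol analysis would have an inflated false positive rate.** This needs failures to be the lowest values and to be removed from one arm only. A rule applied equally to all arms gives no inflation under the null, and under a true difference it works against the better arm.

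The strongest remaining argument is consequence: the intention-to-treat set is primary for every endpoint, so no main conclusion rests on the per-protocol set. That limits how much the point matters but does not remove it. An undefined condition, assessed after allocation is known, makes a supportive analysis hard to interpret in either direction. The missing exclusion for wrong treatment does not depend on how success is read.

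**Conclusion.** The point holds as a defect of definition in the supportive analysis, and it should be corrected. The per-protocol rule contains an undefined post-randomisation condition that permits selection on the endpoints, and its list of major deviations leaves out treatment departures.

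The size cannot be fixed from the documents. It runs from no bias (technical completion, or a common threshold with no true difference) to about 0.10 to 0.17 mm and a type I error of about 9% to 17% (lowest 10% to 20% removed from one arm only). With a true difference of 0.5 mm, a common threshold that fails 10% to 30% of the comparator shrinks the per-protocol difference to between 0.42 and 0.32 mm. These figures assume normal data with the plan's SD of 0.5 mm. The failure fractions are illustrative. The primary analysis and the sample size are unaffected.

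**What to change.** In section 6.1:

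- Delete 'successful', or replace it with surgery completed with the allocated materials as described in section 3.1 (membrane alone in group B), judged without reference to healing or bone gain.
- Add receipt of non-allocated membrane or graft to the major deviations.
- For the CBCT endpoint only, require both scans, with Visit 7 inside its window. Applying this to every endpoint would needlessly drop subjects who have usable inflammation, infection and dehiscence data from the earlier visits.
- State that per-protocol membership is settled before outcomes are known.

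Separately, reconcile the definition of enrolment in section 3.1 with section 3.2.1.3, so that it is clear whether an ineligible but treated subject counts as enrolled.

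The cost is small: rewording the definition, and a check of device reference and lot numbers (section 3.3), deviation records (section 4.7) and visit dates. The per-protocol set for the CBCT endpoint may be slightly smaller. A subject without both scans has no change score in any case, since section 6.1 does not estimate missing data, so the window is the main added restriction.

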3.4 Method of assigning subjects to treatment groups

Subject numbers (subject ID) will be consecutively allocated in series at day of inclusion (Visit 1). Subjects at center 1 will receive numbers starting at 101 and subjects at center 2 will receive numbers starting at 201. Enrollment will continue until 30 subjects at each center have been allocated a subject ID. If a subject discontinues, the subject number will not be reused.

Subjects will be randomized at day of alveolar bone regeneration (Visit 3). At Visit 2 all study sites in all subjects are considered equivalent. The randomization schedule will be generated using a validated computerized randomization system under the responsibility of the investigatory team. The randomization assignment will be concealed via envelope until the surgical date. Randomization will be stratified by center and smoking habit, i.e. each center will have 10 subjects in each group A, B and C, respectively with an equal number of subjects with current tobacco consumption per group. Each subject will be treated according to the treatment code in the envelope. The allocation will be revealed to the clinician only following flap elevation for the alveolar regeneration procedure.

The randomization code envelopes will be stored at each center by designated research staff.

Pre-study, concomitant and post-study treatment(s)

Systemic corticosteroids or any other medication that would compromise post-operative healing and/or bone healing are not allowed.

After surgery, mouth rinsing with 0.12% non-alcohol chlorhexidine rinse will be subscribed according to local routines.

Subjects will be given post-surgical instructions with regards to diet and oral hygiene. Oral hygiene instructions will be given to the subjects at all study visits.

Other medication, which is considered necessary for the subject's safety and well-being, may be given at the discretion of the investigator(s). The administration of all medication (excluding dietary supplements) must be recorded in the appropriate sections of the CRF.

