4.2.1.1.2 Derivation or calculation of variable

The mid-alveolar point positioned on a tangent drawn from the mesial and distal adjacent tooth CEJs will be used as a reference point for assessment of dimensional bone changes in the Z-axis (bone width) and Y-axis (bone height). The changes in the bone dimensions between baseline (Visit 2) and 6 months (Visit 7) will be measured. The change for each study site will be compared longitudinally and the average for each treatment group will be calculated and compared among treatment groups.

Secondary outcome variables

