In order to harmonize the use and handling of the graft materials, training will be conducted prior to study start at each center.

Subgroup analyses

No subgroup analyses are planned.

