6.2 Method of statistical analysis

Primary objective

The primary objective is to compare dimensional bone changes from baseline (Visit 2) to six months (Visit 7) occurring in a single bound edentulous space following alveolar bone regeneration using three different techniques.

Assume the change (in the mid-buccal horizontal bone dimensions from baseline to six months) is denoted C_A , C_B and C_C , for group A, B and C, respectively. The null-hypotheses (two) is then to test if:

$$H_0: C_A = C_i \quad (i = B \text{ and } C, \text{ respectively})$$

can be rejected and hence

$$H_1: C_A \neq C_i \quad (i = B \text{ and } C, \text{ respectively})$$

accepted.

H_0 will be tested by means of the Wilcoxon rank sum test. A p-value less than 5% will be regarded statistically significant.

Secondary objectives

Secondary objectives of the study are to evaluate and compare clinical healing parameters between different grafting techniques (i.e. to compare between groups A, B, and C):

- Inflammation by assessing the presence or absence of soft tissue erythema within 3 mm from the crestal incision at 1 week, 2 weeks, 4 weeks, and 6 months following bone augmentation. The chi-squared analysis will be used.
- Infection by determining the presence or absence of suppuration or soft tissue fluctuance at 1 week, 2 weeks, 4 weeks, and 6 months following bone augmentation. The chi-squared analysis will be used.
- Soft tissue complications by determining the presence or absence of membrane exposure or soft tissue dehiscence at 1 week, 2 weeks, 4 weeks, and 6 months following bone augmentation. The chi-squared analysis will be used.

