6.3 Determination of sample size

A sample size of 20 participants per treatment group was selected following power calculations and allowing for 10% patient dropout. A sample size of 18 patients was calculated for the primary outcome variable (horizontal bone changes) with the assumption that the detectable difference would amount to 0.5 mm with a standard deviation of 0.5. The type I error probability was set at 0.05 and the statistical power was set at 80%.

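### Randomisation is stratified by centre and smoking, but the primary Wilcoxon test adjusts for neither, nor for the baseline bone dimension; adjusting would be a near-free gain in power.

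*Combined protocol and SAP*

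**What the plan says.** The design treats centre and smoking as factors to control. Section 3.1 says "The randomization will be per center and based on smoking status", and section 3.4 says "Randomization will be stratified by center and smoking habit", aiming for 10 subjects per group at each centre and equal numbers of current tobacco users per group.

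The analysis uses neither factor. Section 6.1 states "No covariates are judged to influence the outcome of the primary or any of the secondary variables". On centre it argues that no qualitative differences are expected and concludes "Therefore, the primary statistical analyses will not include center in the model". Under section 6.2 the two null hypotheses (A versus B, A versus C) "will be tested by means of the Wilcoxon rank sum test".

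The baseline measurement is part of the outcome. Section 4.2.1.1.2 says "The changes in the bone dimensions between baseline (Visit 2) and 6 months (Visit 7) will be measured". It is not used as a covariate. No adjusted or stratified analysis is specified, even as a sensitivity analysis. Section 6.1 says that a fuller SAP may be written before database lock but does not say it would adjust for anything.

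**The concern.** Stratified randomisation forces the arms to be alike on the stratification factors. If those factors predict outcome, the difference between arms varies less from trial to trial than a test that ignores them assumes. The test is then conservative: its true type I error lies below 5%, and power that the design has already paid for is lost. Omitting the baseline dimension does not affect the type I error, but it also forgoes power if baseline predicts change.

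The plan's reasons for not adjusting are thin. Smoking is a stratification factor, heavier smoking is an exclusion criterion, and section 3.2 limits cigarettes during the study; all this sits poorly with a statement that no covariate matters. For centre, the absence of a qualitative difference does not exclude a quantitative difference in mean gain, and that is enough to lose power. For baseline, measurement error in the Visit 2 scan enters the change score with a negative sign, so some correlation between baseline and change is plausible. The documents do not give its size.

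**Working it through.** **Inputs from the documents.** Difference 0.5 mm and SD 0.5 mm (section 6.3: "with the assumption that the detectable difference would amount to 0.5 mm with a standard deviation of 0.5"); 18 evaluable and 20 enrolled per group (6.3); alpha 0.05 (6.3), two-sided (6.1); power 80% (6.3); two centres, 10 per group at each (3.1).

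**Assumptions.** Section 6.3 does not say whether the SD is total or residual; it is held here as the total within-group SD. R² is the share of that variance explained by a factor; the documents give no value, so a range is used. Two of the 9 evaluable subjects per group per centre are taken to be smokers.

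**Step 1: the plan's own figure.**
- Normal approximation: n = 2(1.960 + 0.842)² × (0.5/0.5)² = 15.7, so 16 per group.
- Exact t-test: 17 per group (power 80.7%).
- Wilcoxon efficiency under normality, 3/π = 0.955: 17/0.955 = 17.8, so 18.
- 10% dropout: 18/0.9 = 20.

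The stated 18 and 20 reproduce.

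**Step 2: why the planned test becomes conservative.** With arms balanced within strata, the variance of the treatment comparison is about (1 − R²) times what the unadjusted test assumes. A nominal 5% normal test then has true size P(|Z| > 1.96/√(1 − R²)):
- R² = 0.1: 1.96/0.949 = 2.07, size about 3.9%.
- R² = 0.2: 1.96/0.894 = 2.19, size about 2.8%.

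The simulated Wilcoxon figures below are a little lower because that test starts at 4.7%, not 5%.

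**Step 3: what adjustment can give.** For a parametric ANCOVA with three covariates, the noncentrality is 0.5/[0.5√(1 − R²)√(2/18)] = 3/√(1 − R²), on 36 − 2 − 3 = 31 degrees of freedom. Power is 82.8% at R² = 0, 86.5% at 0.1 and 90.1% at 0.2, against 83.0% for the unadjusted t-test. The three degrees of freedom therefore cost about 0.2 points by formula. Chance imbalance in baseline costs slightly more in practice.

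**Step 4: simulation.** 18 per group, 9 per group per centre, normal errors, 20,000 runs per cell (simulation error about 0.3 points on power near 80% and 0.15 on size near 5%). Each triplet is Wilcoxon / rank ANCOVA / parametric ANCOVA, in per cent.

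| Assumed R² | Size | Power at 0.5 mm |
|---|---|---|
| Nothing prognostic | 4.7 / 5.2 / 5.1 | 80.3 / 80.0 / 81.7 |
| Centre 0.05 + smoking 0.05 | 3.5 / 4.9 / 4.8 | 80.8 / 82.9 / 84.9 |
| Centre 0.1 | 3.7 / 5.1 / 5.1 | 81.3 / 83.5 / 85.5 |
| Centre 0.2 | 2.5 / 5.1 / 5.0 | 82.1 / 87.1 / 89.0 |
| Centre 0.1 + smoking 0.1 | 2.7 / 4.8 / 4.9 | 82.4 / 87.6 / 89.4 |
| Baseline 0.1 | 4.6 / 5.0 / 4.9 | 80.3 / 83.1 / 85.0 |
| Baseline 0.2 | 4.7 / 4.9 / 4.9 | 80.2 / 86.8 / 89.1 |
| Baseline 0.4 | 4.6 / 4.8 / 4.9 | 80.1 / 93.6 / 95.7 |
| Centre 0.1 + smoking 0.1 + baseline 0.2 | 2.8 / 5.1 / 5.0 | 82.2 / 93.5 / 95.6 |

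**Step 5: non-normal errors, nothing prognostic.** Power is 95.9 / 95.6 / 85.9 with t errors on 3 df and 99.3 / 99.2 / 85.4 with lognormal errors. The rank form keeps the robustness of the planned test; the parametric form does not.

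**Step 6: with dropout.** 20 per arm, 10% random loss, smokers balanced, uneven or absent (6,000 runs, normal errors): rank ANCOVA size 4.4–5.6%. With nothing prognostic its power is 78.1–79.1%, against 79.0–80.8% for the Wilcoxon. With centre 0.1 and baseline 0.1 it is 85.8–87.3% against 80.9–82.6%.

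**Scale of these R² values.** For centre alone, the difference in mean gain between centres is 2 × √R² × 0.5 mm: 0.32 mm at R² = 0.1 and 0.45 mm at 0.2.

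**The case against.** The planned test is pre-specified and valid, and it meets its power target under the stated inputs. Every gain above rests on R² values that the documents do not supply. Several features may keep those values small: "In order to harmonize the use and handling of the graft materials, training will be conducted prior to study start at each center"; one masked analyst reads all scans (4.2.1.1.1); and eligibility limits cigarettes to 10 per day and ridge width to 4 mm (3.2). For centre alone, an R² of 0.1 or 0.2 needs a centre difference equal to 64% or 90% of the 0.5 mm effect the trial is sized for (0.32/0.5 and 0.45/0.5). If section 6.1 is right that nothing is prognostic, the adjusted rank test loses a little power and, after dropout, can fall just below 80%. It also brings a p-value from one model and an interval from another.

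All of that stands. It limits the point to an efficiency and consistency weakness. It does not remove it: the possible loss is 0 to 2 points, the gain is 2 to 11 points in the scenarios above where the strata explain at least 10%, and the choice must be made before anyone knows which case applies. The two-model problem is met by stating in advance which result decides.

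**Conclusion.** The point holds. Design and analysis are not aligned, and adjustment is worth making, but nothing in the plan is invalid and the sample size is not undermined on the reading that 0.5 mm is the total SD. With strata R² of 0.1 to 0.2, the planned test runs at about 3.7% down to 2.5% instead of 5%, and a rank ANCOVA has about 2 to 5 points more power. Baseline R² of 0.1 to 0.2 adds about 3 to 7 points. With nothing prognostic the gain is nil or slightly negative. Apart from the check in Step 5, the figures assume normal errors; the smoker numbers and all R² values are assumptions.

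**What to change.** In section 6.1, delete the sentence that denies any covariate influence and the one that excludes centre. In section 6.2 (and the synopsis, which names the same test), state for the horizontal dimension, for A versus B and A versus C separately:

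1. Rank the change over the two groups. Regress the ranks on treatment, ranked Visit 2 dimension, centre and smoking stratum (main effects only). Test treatment two-sided with the model's residual degrees of freedom. Drop the smoking term if the pair contains no smokers.
2. The baseline covariate is the Visit 2 value of the same CBCT measurement from which change is formed, not the ridge width used for eligibility.
3. The rank ANCOVA p-value decides. Report ANCOVA-adjusted A–B and A–C differences with 95% confidence intervals, and the unadjusted Wilcoxon test as a sensitivity analysis.

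Settle this in the SAP before database lock.

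**Cost.** SAP wording and a few lines of code; every variable is already collected. There are three downsides:
- Three degrees of freedom: 0 to 2 points of power if nothing is prognostic.
- The rank p-value and the ANCOVA interval disagreed on significance in about 2–3% of null trials and 3–5% of trials with the 0.5 mm effect (normal errors), hence the need for item 3.
- The form matters. Comparing rank residuals between groups without charging the covariate degrees of freedom gave size 5.4–6.2% at this sample size.

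**Alternatives.** Parametric ANCOVA as the primary test avoids the two-model problem but can have less power than the Wilcoxon under heavy-tailed or skewed residuals. A van Elteren test over centre by smoking is less attractive: with non-prognostic strata its power was 77.2% against 81.0% for the plain Wilcoxon (6,000 runs).
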